1.2 Secondary Objectives

1.2.1 Phase 1

1.2.2 To observe and record anti-tumor activity. Although the clinical benefit of these drugs has not yet been established, the intent of offering this treatment is to provide a possible therapeutic benefit, and thus the patient will be carefully monitored for tumor response and symptom relief in addition to safety and tolerability.

1.2.3 Phase 2

1.2.3.1 To compare the efficacy of the combination of Hu5F9-G4 (magrolimab) and mogamulizumab versus mogamulizumab alone with respect to the following endpoints:

- Overall Response Rate (ORR); Overall Response Rate lasting at least 4 months (ORR4); Overall Response Rate lasting at least 12 months (ORR12)
- Duration of response (DOR)
- Progression-free survival (PFS)
- Time to next treatment (TTNT)

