Phase 2 Power and Sample Size: We anticipate a lower ORR6 response rate for the control mogamulizumab arm of this trial to be lower than that for MAVORIC (Kim *et al*, 2018). This is because mogamulizumab is now FDA-approved and is increasingly being utilized in the treatment of patients with SS in particular, where higher response rates were seen in the MAVORIC trial. Therefore, we anticipate that referrals to this trial will be more skewed towards MF than MAVORIC where Sezary patients comprised 45% of the intention-to-treat (ITT) population. We have therefore estimated that the control arm of this cohort will have an ORR6 of 16% for the purposes of the power calculation, with 30% ORR6 in the SS patients and 10% in the MF patients, who we estimate will comprise 70% of the trial (resulting in a combined ORR6 of 16%). With 82 patients (41 in each arm), and assuming the 2 strata with SS have an ORR6 of 30% and the 2 strata with MF have an ORR6 of 10%, and looking to detect an odds ratio of 3.2 associated with the addition of Hu5F9-G4 (magrolimab), there is 86% power to detect this effect size with 41 patients in each treatment arm, with a type I error (one-sided) of 0.15. The choice of the type I error is based on (Rubinstein *et al.*, 2005). This odds ratio is associated with detecting an improvement from 16% to 36% in the ORR6. This calculation is based on the Mantel-Haenszel (Cochran) test for 2x2 tables for 4 strata (based on MF vs SS and Stage) and calculated with nQuery+nTerim 4.0 (2015).

In addition, if the Sezary patients are more prevalent than we anticipate, reaching a percentage of

patients reflected in the MAVORIC trial (45%), the combined ORR6 is 19% and the power increases from 86% to 88%.

Interim Futility Analysis: A planned interim futility analysis will be performed as per the Wieand rule. When 50% of the patients are evaluable, if the ORR6 of the combination is not superior to the single agent, accrual will hold.

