9.4 Analysis of Secondary Endpoints

The analysis plan for the secondary objectives will be as follows:

Table 5: Analysis of Secondary Endpoints

Secondary Endpoint	Statistical Method
ORR, ORR4, ORR12	Chi-squared
PFS, DOR, TTNT	Kaplan-Meier method; Log- rank

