12.2 Definitions of Study Endpoints

Overall Response Rate (ORR): ORR is defined as the proportion of patients who have a partial or complete response to therapy as defined by the global response score.

Duration of Response (DOR): DOR is defined as the duration of overall response is measured from the time measurement criteria are met for CR or PR (whichever is first recorded) until the first date that recurrence or PD is objectively documented.

Overall Response Rate 4 (ORR4): ORR4 is defined as the proportion of patients who have a partial or complete response to therapy AND a duration of response \geq 4 months.

Overall Response Rate 6 (ORR6): ORR6 is defined as the proportion of patients who have a partial or complete response to therapy AND a duration of response \geq 6 months.

Overall Response Rate 12 (ORR12): ORR12 is defined as the proportion of patients who have a partial or complete response to therapy AND a duration of response \geq 12 months.

Progression-Free Survival (PFS): PFS is defined as the duration of time from start of treatment to time of progression or death, whichever occurs first.

Time to next treatment (TTNT): TTNT is defined as the duration of time from the start of treatment on this protocol to time of the next anti-neoplastic therapy.

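### The planned log-rank test on duration of response compares responders with responders, so it is not a randomised comparison and can point against a combination that raises ORR6

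*Combined protocol and SAP*

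**What the plan says.** Section 1.2 lists DOR among the phase 2 secondary endpoints, under the aim "To compare the efficacy of the combination of Hu5F9-G4 (magrolimab) and mogamulizumab versus mogamulizumab alone with respect to the following endpoints". It is therefore planned as a between-arm efficacy comparison.

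Table 5 in section 9.4 gives the method for PFS, DOR and TTNT together: "Kaplan-Meier method; Log- rank". It names no analysis population and no significance level for any of the three.

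Section 12.2 defines the endpoint: "DOR is defined as the duration of overall response is measured from the time measurement criteria are met for CR or PR". PFS and TTNT, by contrast, run from the start of treatment.

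No section calls the DOR comparison descriptive, gives non-responders a value, or adjusts for selection on response.

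**The concern.** Every treated patient has a PFS and a TTNT. Only a patient who reaches CR or PR has a DOR. A log-rank test on DOR therefore sets the combination arm's responders against the control arm's responders.

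Randomisation makes the full arms comparable. It does not make the responders comparable, because response happens after randomisation and is what the added drug is meant to change. Section 9.1 plans for ORR6 to rise from 16% to 36%. If that happens, the combination's responder group contains many patients who would not have responded on mogamulizumab alone. If their responses are shorter than those of patients who respond either way, the combination's DOR curve falls below the control curve although no patient is worse off.

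At stake is the reading of one secondary result: a DOR p-value or hazard ratio that looks unfavourable, or merely flat, beside a real gain in durable response.

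**Working it through.** **The plan's own figures.** The documents give no power, event count or effect size for DOR. Two related figures can be reproduced.

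- *ORR6 power* (section 9.1: 41 per arm, odds ratio 3.2, one-sided 0.15). MF: 10% becomes 26.2%, 28.7 patients per arm. SS: 30% becomes 57.8%, 12.3 per arm. With weights of half the per-arm count, the summed difference is 14.35 × 0.1623 + 6.15 × 0.2783 = 4.04. The null and alternative standard deviations are 1.909 and 1.852. Power = Φ[(4.04 − 1.036 × 1.909) / 1.852] = Φ(1.11) = 86.7%, against the stated 86%. This calculation does not involve DOR.
- *Historical ORR6.* Section 2.3.1 gives mogamulizumab ORR 28% and median DOR 14.1 months in MAVORIC. With exponential durations, 0.28 × 2^(−6/14.1) = 0.28 × 0.745 = 20.8%, against the 21% in section 9.1. The exponential model is adequate for an illustration.

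**Why the direction can reverse.** Suppose 28% respond in either arm and the combination adds 20 points. Let m be the median DOR in added responders, and k the factor by which magrolimab lengthens responses that would occur anyway. At the start of response, the ratio of the hazard of losing response, combination v control responders, is

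(28/k + 20 × 14.1/m) / 48.

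With k = 1 this is 84.4/48 = 1.76 for m = 5, 56.2/48 = 1.17 for m = 10, and 48/48 = 1.00 for m = 14.1. Over the same scenarios true ORR6 rises from 20.8% to 20.8 + 20 × 2^(−6/5) = 29.6% (m = 5) or 20.8 + 20 × 2^(−6/10) = 34.0% (m = 10).

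**Simulation of the Table 5 test.** 41 per arm, 3,000 trials per scenario, exponential DOR, censoring uniform on 9–33 months (assumed), log-rank among responders only. There are about 11.5 v 20 responders. "Nominally worse" uses one-sided 0.15, borrowed from ORR6.

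| Added responders' median (m) | Existing responses (k) | Starting hazard ratio | Points against combination | Nominally worse |
|---|---|---|---|---|
| 5 months | unchanged | 1.76 | about 81% | about 43% |
| 10 months | unchanged | 1.17 | about 62% | about 22% |
| 14.1 months | unchanged | 1.00 | about 49% | near nominal |
| 10 months | × 1.5 | 46.9/48 = 0.98 | 43% | – |
| 7 months | × 2 | 54.3/48 = 1.13 | 44% | – |
| 10 months | × 2 | 42.2/48 = 0.88 | 33% | – |

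In the 5- and 10-month rows with existing responses unchanged, the test is nominally in favour of the combination in only about 3–10% of trials. With no added responders and equal durations the test holds its level, about 15% each way, so the shift comes from who enters the comparison. Lengthening of 25% with m = 6 (24-month follow-up) still gave 66% against.

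**At the design alternative.** ORR6 of 16% corresponds to a control ORR of 0.16/0.745 = 21.5%. Reaching 36% needs 0.20/2^(−6/9) = 31.7 points of added responders at m = 9, or 0.20/2^(−6/6) = 40 points at m = 6. With existing responses unchanged and 24 months of follow-up (assumed):

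- m = 9: about 9 v 22 responders; points against in 70%, nominally worse in 30%.
- m = 6: about 9 v 25 responders; points against in 86%, nominally worse in 53%.
- m = 14.1: points against in 49%. The test shows nothing although ORR6 has risen by 20 points.

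On the same data, mean months in response over 24 months with non-responders scored zero are 3.0 v 6.5 (m = 9) and 3.0 v 6.2 (m = 6). That comparison points the wrong way in 2.5% of trials in both cases.

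**The case against.** **Duration is already compared validly.** The primary endpoint ORR6 and the secondary ORR4 and ORR12 are proportions of patients, not of responders, and section 9.1 counts patients without an assessment as ORR6 failures. Section 2.4.5 prefers the composite because DOR and similar endpoints are hard to read in CTCL. This stands as mitigation. The reason given there is early switching of therapy, however, not selection on response, and the DOR test remains in Table 5.

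**The adverse figures rest on one-directional assumptions.** This stands. They need shorter responses in added responders and little or no lengthening of existing ones. The documents give neither. A reader might infer that the test *will* point against the combination, or that 62–81% is a forecast. The documents do not support that.

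**No decision depends on DOR.** This also stands. A reader might infer that the DOR test could distort the go/no-go decision. The sample size and futility rule in section 9.1 rest on ORR6, and DOR has no alpha, power or place in any decision rule.

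**Section 9.5.2.** A reader might take its rule that conclusions rest on all eligible patients as forbidding the DOR test outright. That text concerns the response-rate analysis and exclusions for protocol deviations, so it supports the principle only by analogy.

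**Reporting DOR among responders is customary.** Agreed. The defect is the between-arm test, not the per-arm summary.

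**Conclusion.** The point holds. As written, the plan tests a between-arm difference on an outcome that only responders have, and the test does not estimate an effect of treatment in the randomised arms. That conclusion needs no simulation.

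The size is conditional. If existing responses are unchanged and added responders have medians of 5–10 months, the test leans clearly against a beneficial combination. If durations are equal it has no lean but is blind to the gain. If existing responses lengthen enough, it leans in favour. The 33–44% figures belong to the three tabulated combinations; shorter added durations or less lengthening give higher shares. Since the documents fix none of these quantities, the direction of the DOR result cannot be read as benefit or harm.

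The scope is one secondary endpoint. PFS and TTNT in the same row start at treatment and do not share the defect.

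**What to change.** In Table 5, give DOR its own row: Kaplan-Meier median with confidence interval by arm, among responders, descriptive, with no between-arm p-value. Keep the log-rank for PFS and TTNT.

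State that between-arm conclusions about duration rest on ORR4, ORR6 and ORR12. Keep every patient of the section 9.1 analysis population in the denominator: those who start treatment for the primary analysis, with ITT as secondary. Table 5 names no population for ORR4 and ORR12, so this should be written in.

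Mean time in response over a fixed window, with non-responders scored zero, is an optional addition that uses data already collected.

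The cost is a wording change and one fewer secondary p-value. Sample size, conduct and the primary analysis do not change.

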9.5 Reporting and Exclusions

9.5.1 Evaluation of Toxicity

All patients will be evaluable for toxicity from the time of their first treatment with Hu5F9-G4 (magrolimab).

9.5.2 Evaluation of Response

All patients included in the study must be assessed for response to treatment, even if there are major protocol treatment deviations. Each patient will be assigned one of the following categories: 1) complete response, 2) partial response, 3) stable disease, 4) progressive disease, 5) early death from malignant disease, 6) early death from toxicity, 7) early death because of other cause, or 9) unknown (not assessable, insufficient data). [Note: By arbitrary convention, category 9 usually designates the “unknown” status of any type of data in a clinical database.]

NCI Protocol #: 10384

Version Date: September 5, 2023

All of the patients who met the eligibility criteria (with the possible exception of those who received no study medication) should be included in the main analysis of the response rate. Patients in response categories 4-9 should be considered to have a treatment failure (disease progression). Thus, an incorrect treatment schedule or drug administration does not result in exclusion from the analysis of the response rate. Precise definitions for categories 4-9 will be protocol specific.

All conclusions should be based on all eligible patients. Subanalyses may then be performed on the basis of a subset of patients, excluding those for whom major protocol deviations have been identified (e.g., early death due to other reasons, early discontinuation of treatment, major protocol violations, etc.). However, these subanalyses may not serve as the basis for drawing conclusions concerning treatment efficacy, and the reasons for excluding patients from the analysis should be clearly reported.

9.6 Data Safety Monitoring Board

The conduct of this study will be overseen by the ETCTN DSMB. The DSMB will be responsible for recommendations to the Principal Investigator and NCI regarding possible trial closure and/or early reporting of the study. The study team (with the exception of the study statistician) will not have access to the summary outcome data until released by the DSMB.

10. ADVERSE EVENTS: LIST AND REPORTING REQUIREMENTS

Adverse event (AE) monitoring and reporting is a routine part of every clinical trial. The following list of AEs (Section 10.1) and the characteristics of an observed AE (Sections 10.2 and 10.3) will determine whether the event requires expedited reporting via the CTEP Adverse Event Reporting System (CTEP-AERS) **in addition** to routine reporting.

10.1 Comprehensive Adverse Events and Potential Risks List(s) (CAEPRs)

10.1.1 CAEPR for CTEP IND Agent

10.1.1.1 CAEPR for Hu5F9-G4 (magrolimab)

Comprehensive Adverse Events and Potential Risks list (CAEPR) for Hu5F9-G4 (magrolimab, NSC 809249)

The Comprehensive Adverse Events and Potential Risks list (CAEPR) provides a single list of reported and/or potential adverse events (AE) associated with an agent using a uniform presentation of events by body system. In addition to the comprehensive list, a subset, the Specific Protocol Exceptions to Expedited Reporting (SPEER), appears in a separate column and is identified with bold and italicized text. This subset of AEs (SPEER) is a list of events that are protocol specific exceptions to expedited reporting to NCI (except as noted below). Refer to the 'CTEP, NCI Guidelines: Adverse Event Reporting Requirements'

NCI Protocol #: 10384

Version Date: September 5, 2023

http://ctep.cancer.gov/protocolDevelopment/electronic_applications/docs/aeguidelines.pdf for further clarification. Frequency is provided based on 579 patients. Below is the CAEPR for Hu5F9-G4 (magrolimab).

NOTE: Report AEs on the SPEER **ONLY IF** they exceed the grade noted in parentheses next to the AE in the SPEER. If this CAEPR is part of a combination protocol using multiple investigational agents and has an AE listed on different SPEERs, use the lower of the grades to determine if expedited reporting is required.

Version 2.1, May 24, 2022¹

Adverse Events with Possible Relationship to Hu5F9-G4 (Magrolimab) (CTCAE 5.0 Term) [n= 579]			Specific Protocol Exceptions to Expedited Reporting (SPEER)
Likely (>20%)	Less Likely (<=20%)	Rare but Serious (<3%)	
BLOOD AND LYMPHATIC SYSTEM DISORDERS			
Anemia			Anemia (Gr 2)
GASTROINTESTINAL DISORDERS			
	Diarrhea		Diarrhea (Gr 2)
	Nausea		Nausea (Gr 2)
	Vomiting		Vomiting (Gr 2)
GENERAL DISORDERS AND ADMINISTRATION SITE CONDITIONS			
	Chills		Chills (Gr 2)
	Fatigue		Fatigue (Gr 2)
	Fever		Fever (Gr 2)
INJURY, POISONING AND PROCEDURAL COMPLICATIONS			
Infusion related reaction			Infusion related reaction (Gr 2)
INVESTIGATIONS			
	Blood bilirubin increased		
	Platelet count decreased		
METABOLISM AND NUTRITION DISORDERS			
	Anorexia		
	Hypomagnesemia		
NERVOUS SYSTEM DISORDERS			
	Headache		Headache (Gr 2)
SKIN AND SUBCUTANEOUS TISSUE DISORDERS			
	Dry skin		
	Rash acneiform		

¹This table will be updated as the toxicity profile of the agent is revised. Updates will be distributed to all Principal Investigators at the time of revision. The current version can be obtained by contacting [contact]. Your name, the name of the investigator, the protocol and the agent should be included in the e-mail.

Adverse events reported on Hu5F9-G4 (Magrolimab) trials, but for which there is insufficient evidence to suggest that there was a reasonable possibility that Hu5F9-G4 (Magrolimab) caused the adverse event:

BLOOD AND LYMPHATIC SYSTEM DISORDERS - Febrile neutropenia; Thrombotic thrombocytopenic purpura

GASTROINTESTINAL DISORDERS - Colitis; Mucositis oral

INFECTIONS AND INFESTATIONS - Sepsis

MUSCULOSKELETAL AND CONNECTIVE TISSUE DISORDERS - Back pain; Pain in extremity

RESPIRATORY, THORACIC AND MEDIASTINAL DISORDERS - Dyspnea; Hypoxia

SKIN AND SUBCUTANEOUS TISSUE DISORDERS - Rash maculo-papular

Note: Hu5F9-G4 (Magrolimab) in combination with other agents could cause an exacerbation of any adverse event

NCI Protocol #: 10384

Version Date: September 5, 2023

currently known to be caused by the other agent, or the combination may result in events never previously associated with either agent.

10.1.2 CAEPR for Commercial Agent

10.1.2.1 CAEPR for Mogamulizumab

Comprehensive Adverse Events and Potential Risks list (CAEPR) for KW-0761 (mogamulizumab, NSC 791064)

The Comprehensive Adverse Events and Potential Risks list (CAEPR) provides a single list of reported and/or potential adverse events (AE) associated with an agent using a uniform presentation of events by body system. In addition to the comprehensive list, a subset, the Specific Protocol Exceptions to Expedited Reporting (SPEER), appears in a separate column and is identified with bold and italicized text. This subset of AEs (SPEER) is a list of events that are protocol specific exceptions to expedited reporting to NCI (except as noted below). Refer to the 'CTEP, NCI Guidelines: Adverse Event Reporting Requirements' http://ctep.cancer.gov/protocolDevelopment/electronic_applications/docs/aeguidelines.pdf for further clarification. *Frequency is provided based on 4759 patients.* Below is the CAEPR for KW-0761 (mogamulizumab).

NOTE: Report AEs on the SPEER **ONLY IF** they exceed the grade noted in parentheses next to the AE in the SPEER. If this CAEPR is part of a combination protocol using multiple investigational agents and has an AE listed on different SPEERs, use the lower of the grades to determine if expedited reporting is required.

Version 2.3, September 15, 2019¹

Adverse Events with Possible Relationship to KW-0761 (mogamulizumab) (CTCAE 5.0 Term) [n= 4759]			Specific Protocol Exceptions to Expedited Reporting (SPEER)
Likely (>20%)	Less Likely (<=20%)	Rare but Serious (<3%)	
CARDIAC DISORDERS			
		Chest pain - cardiac	
		Myocardial infarction	
		Myocarditis ²	
		Restrictive cardiomyopathy	
GASTROINTESTINAL DISORDERS			
	Nausea		Nausea (Gr 2)
GENERAL DISORDERS AND ADMINISTRATION SITE CONDITIONS			
	Fatigue		Fatigue (Gr 2)
	Fever		Fever (Gr 2)
	Flu like symptoms ²		
IMMUNE SYSTEM DISORDERS			
	Allergic reaction		
		Anaphylaxis ³	
		Immune system disorders - Other (graft versus host disease) ⁴	
INFECTIONS AND INFESTATIONS			

Adverse Events with Possible Relationship to KW-0761 (mogamulizumab) (CTCAE 5.0 Term) [n= 4759]			Specific Protocol Exceptions to Expedited Reporting (SPEER)
Likely (>20%)	Less Likely (<=20%)	Rare but Serious (<3%)	
	Infection ⁵		
INJURY, POISONING AND PROCEDURAL COMPLICATIONS			
	Infusion related reaction ³		Infusion related reaction ³ (Gr 2)
INVESTIGATIONS			
	Alanine aminotransferase increased ^{2,6}		
	Alkaline phosphatase increased ^{2,6}		
	Aspartate aminotransferase increased ^{2,6}		
	Blood bilirubin increased ^{2,6}		
	GGT increased ^{2,6}		
	Lymphocyte count decreased ²		Lymphocyte count decreased ² (Gr 2)
	Neutrophil count decreased ²		Neutrophil count decreased ² (Gr 2)
	Platelet count decreased ²		Platelet count decreased ² (Gr 2)
	White blood cell decreased ²		White blood cell decreased ² (Gr 2)
METABOLISM AND NUTRITION DISORDERS			
		Tumor lysis syndrome	
MUSCULOSKELETAL AND CONNECTIVE TISSUE DISORDERS			
	Arthritis ²		
NERVOUS SYSTEM DISORDERS			
	Peripheral motor neuropathy ²		
RESPIRATORY, THORACIC AND MEDIASTINAL DISORDERS			
	Pneumonitis ²		
SKIN AND SUBCUTANEOUS TISSUE DISORDERS			
		Erythema multiforme ²	
	Rash maculo-papular ²		Rash maculo-papular ² (Gr 2)
		Skin and subcutaneous tissue disorders - Other (drug eruption, toxic skin eruption) ²	
	Skin hypopigmentation ²		
		Stevens-Johnson syndrome ²	
		Toxic epidermal necrolysis ²	

¹This table will be updated as the toxicity profile of the agent is revised. Updates will be distributed to all Principal Investigators at the time of revision. The current version can be obtained by contacting [contact]. Your name, the name of the investigator, the protocol and the agent should be included in the e-mail.

²Immune-mediated adverse reactions have been reported in patients receiving KW-0761 (mogamulizumab). Adverse events potentially related to KW-0761 (mogamulizumab) may be manifestations of immune-mediated adverse events. In clinical trials, most immune-mediated adverse reactions were reversible and managed with interruptions of KW-0761 (mogamulizumab), administration of corticosteroids and supportive care.

³Infusion reactions, including high-grade hypersensitivity reactions, anaphylaxis, and cytokine release syndrome, which have been observed following administration of KW-0761 (mogamulizumab), may manifest as fever, chills, shakes, itching, rash, hypertension or hypotension, or difficulty breathing during and immediately after administration of KW-0761 (mogamulizumab).

⁴Acute graft-versus-host disease has been observed in patients treated with KW-0761 (mogamulizumab) who subsequently received hematopoietic stem cell transplants.

⁵Infection may include any of the infection sites under the INFECTIONS AND INFESTATIONS SOC.

⁶Symptoms of hepatic dysfunction may include Alanine aminotransferase increased, Alkaline phosphatase increased, Aspartate aminotransferase increased, Blood bilirubin increased, and GGT increased under the INVESTIGATIONS SOC.

Adverse events reported on KW-0761 (mogamulizumab) trials, but for which there is insufficient evidence to suggest that there was a reasonable possibility that KW-0761 (mogamulizumab) caused the adverse event:

BLOOD AND LYMPHATIC SYSTEM DISORDERS - Anemia; Disseminated intravascular coagulation; Febrile neutropenia; Hemolysis; Thrombotic thrombocytopenic purpura

CARDIAC DISORDERS - Atrial fibrillation; Sinus tachycardia; Supraventricular tachycardia

EYE DISORDERS - Retinal vascular disorder

GASTROINTESTINAL DISORDERS - Abdominal pain; Cheilitis; Colitis²; Constipation; Diarrhea; Gastritis; Mucositis oral; Vomiting

GENERAL DISORDERS AND ADMINISTRATION SITE CONDITIONS - Chills; Death NOS; Edema limbs; Generalized edema; Malaise; Multi-organ failure

HEPATOBILIARY DISORDERS - Cholecystitis; Hepatic failure; Hepatobiliary disorders - Other (bile duct stone); Hepatobiliary disorders - Other (hepatitis)

INVESTIGATIONS - Blood lactate dehydrogenase increased²; CPK increased; Lipase increased; Serum amylase increased; Weight loss

METABOLISM AND NUTRITION DISORDERS - Acidosis; Anorexia; Dehydration; Hypercalcemia; Hyperglycemia; Hyperkalemia; Hypoalbuminemia; Hypocalcemia; Hypokalemia; Hypomagnesemia; Hyponatremia; Hypophosphatemia; Metabolism and nutrition disorders - Other (diabetes mellitus)

MUSCULOSKELETAL AND CONNECTIVE TISSUE DISORDERS - Arthralgia; Flank pain; Generalized muscle weakness; Musculoskeletal and connective tissue disorder - Other (tendonitis); Myositis

NEOPLASMS BENIGN, MALIGNANT AND UNSPECIFIED (INCL CYSTS AND POLYPS) - Treatment related secondary malignancy

NERVOUS SYSTEM DISORDERS - Depressed level of consciousness; Encephalopathy; Headache; Nervous system disorders - Other (altered state of consciousness); Nervous system disorders - Other (cerebellar syndrome); Paresthesia; Seizure

RENAL AND URINARY DISORDERS - Acute kidney injury

RESPIRATORY, THORACIC AND MEDIASTINAL DISORDERS - Adult respiratory distress syndrome; Cough; Dyspnea; Hypoxia; Pleural effusion; Respiratory failure

SKIN AND SUBCUTANEOUS TISSUE DISORDERS - Alopecia; Dry skin; Erythroderma; Hyperhidrosis; Palmar-plantar erythrodysesthesia syndrome; Photosensitivity; Pruritus; Rash acneiform; Skin and subcutaneous tissue disorders - Other (lichenoid keratosis); Urticaria

VASCULAR DISORDERS - Hypertension²; Hypotension²

Note: KW-0761 (mogamulizumab) in combination with other agents could cause an exacerbation of any adverse event currently known to be caused by the other agent, or the combination may result in events never previously associated with either agent.

